5 STUDY ACTIVITIES

5.1 Eligibility Criteria

Subjects must meet all of the following criteria to be included in the study. Anything other than a positive response to the questions below will result in exclusion from study participation.

Consent

- 1. Subject must voluntarily **sign and date an informed consent**, approved by an independent ethics committee (IEC)/institutional review board (IRB), prior to the initiation of any screening or study-specific procedures.

Demographic and Laboratory Assessments

- 2. Adult **male or female**, at least 18 years old at time of the baseline visit.
- 3. **Laboratory values** meeting the following criteria within the screening period prior to the first dose of study drug:
 - Hemoglobin \geq 8 g/dL;
 - Serum aspartate transaminase (AST) and alanine transaminase (ALT) $\leq 2 \times$ upper limit of normal (ULN).
- 4. Are willing and able to comply with procedures required in this protocol.

- ✓ 5. Estimated glomerular filtration rate (eGFR) calculated by Cockcroft-Gault ≥ 90 mL/min at the Screening visit.

Disease/Condition Activity

- ✓ 6. Diagnosis of UC for at least 90 days prior to Baseline. Appropriate documentation of biopsy results consistent with the diagnosis of UC in the assessment of the investigator, must be available prior to enrollment.
- ✓ 7. Subject meets the following disease activity criteria: Active UC with an Adapted Mayo score of 5 to 9 points and ESS of 2 to 3 (confirmed by central review prior to enrollment).

Subject History

- ✓ 8. Subject must not have an active, chronic, or recurrent infection that based on the investigator's clinical assessment makes the subject an unsuitable candidate for the study, or the following:
 - Subject must not currently be positive with *C. difficile* toxin as identified during Screening or another known intestinal pathogen;
 - Subject must not be infected with human immunodeficiency virus (HIV);
 - Subject must not have active hepatitis B or hepatitis C (as defined in the Operations Manual);
 - Subject must not have evidence of active tuberculosis (TB) or meet TB exclusionary parameters (See specific requirements for TB testing in Section 3.13 of the Operations Manual).

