- ✓ 9. No known active SARS-CoV-2 infection. If a subject has signs/symptoms suggestive of SARS-CoV-2 infection, the subject must have a negative molecular (e.g., PCR) test or 2 negative antigen test results at least 24 hours apart. Note: SARS CoV-2 diagnostic tests should be applied following local requirements/recommendations.
 - Subjects who do not meet SARS-CoV-2 infection eligibility criteria may only resume screening for the study after they meet the following SARS-CoV-2 infection viral clearance criteria:
 - At least 10 days since the first positive test result has passed in asymptomatic patients or at least 10 days since recovery, defined as resolution of fever without use of antipyretics and improvement in symptoms.
- ✓ 10. No current diagnosis of CD or inflammatory bowel disease-unclassified (IBD-U).
- ✓ 11. No extent of inflammatory disease limited to the rectum as assessed by screening endoscopy.
- ✓ 12. No currently known complications of UC such as:
 - fulminant colitis,
 - toxic megacolon,

- previous colectomy (total or subtotal), or
- any other manifestation that might require surgery while enrolled in the study.

✓ 13. Subject must not have current suicidal ideation with plan within the prior month, via answering "yes" to questions 4 or 5 to the suicidal ideation portion of the Columbia-Suicide Severity Rating Scale (C-SSRS) completed at Screening and Baseline, or any history of suicide attempt(s) within the last 2 years.

✓ 14. No history of seizures (excluding history of a single childhood febrile seizure before age 5), epilepsy, convulsions, significant head injury, or other significant neurologic conditions.

✓ 15. Subjects must not have an ostomy or ileoanal pouch.

✓ 16. No history of radiation colitis or ischemic colitis.

✓ 17. No history of any malignancy except for successfully treated non metastatic cutaneous squamous cell or basal cell carcinoma or localized carcinoma in situ of the cervix.

✓ 18. No history of clinically significant (per investigator's judgment) drug or alcohol abuse within the last 12 months.

✓ 19. No history of clinically significant medical conditions or any other reason that the investigator determines would interfere with the subject's participation in this study or would make the subject an unsuitable candidate to receive study drug.

✓ 20. No history of an allergic reaction or significant sensitivity to constituents of the study drug (and its excipients) and/or other products in the same class.

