 - Signs and symptoms of persistently active disease despite a history of at least one 90 day regimen of oral azathioprine (AZA) (\geq 1.5 mg/kg/day) rounded to the nearest available tablet or half tablet formulation, 6 mercaptopurine (6MP) (\geq 1 mg/kg/day) rounded to the nearest available tablet or half tablet formulation (or a documented 6-thioguanine nucleotide [6-TGN] level of 230 – 450 pmol/8 \times 10⁸ red blood cell [RBC] count or higher on the current dosing regimen), or injectable methotrexate ([MTX] \geq 15 mg/week subcutaneous [SC] or intramuscular [IM]), OR
 - History of intolerance to at least one immunosuppressant (including, but not limited to nausea/vomiting, abdominal pain, pancreatitis, liver enzyme abnormalities, lymphopenia, infection).
- Note: Oral MTX use is allowed during the study, however prior or current use of oral MTX is not sufficient for inclusion into the study unless these subjects were previously treated with aminosalicylates, corticosteroids, immunosuppressants (azathioprine [AZA] or 6-MP) or biologic and targeted immunomodulatory therapy and have inadequate response to, loss of response to or intolerance to the therapy as defined above.
- Targeted Immunomodulatory Therapy (including biologics and non-biologics) for UC
 - Signs and symptoms of persistently active disease despite a history of any of the following:
 - Infliximab: At least one 6-week induction regimen of infliximab (\geq 5 mg/kg intravenous [IV] at Weeks 0, 2, and 6);
 - Adalimumab: At least one 4-week induction regimen of adalimumab (one 160 mg SC dose at Week 0, followed by one 80 mg SC dose at Week 2),
 - Golimumab: At least one 4-week induction regimen of golimumab (200 mg SC at Weeks 0 and 100 mg SC at Week 2);
 - Vedolizumab: At least one 6-week induction regimen of vedolizumab (300 mg IV at Weeks 0, 2, and 6);

- Ustekinumab: At least an induction regimen of a single weight-based infusion dose of ustekinumab (260 mg [\leq 55 kg] or 390 mg [$>$ 55 to \leq 85 kg] or 520 mg [$>$ 85 kg] IV);
- Tofacitinib: At least one 8-week induction regimen of tofacitinib (10 mg PO BID);
- Ozanimod: At least one 10-week induction regimen of ozanimod (0.92 mg PO once a day beginning with dose titration);
- Upadacitinib: At least one 8-week induction regimen of upadacitinib (45 mg PO once daily);
- Filgotinib (EU only): At least one 10-week induction regimen of filgotinib (200 mg PO once daily);

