- Recurrence of symptoms during scheduled, maintenance dosing following prior clinical benefit (discontinuation despite clinical benefit does not qualify); or
- History of intolerance to at least one biologic agent or targeted immunomodulatory therapy (including, but not limited to infusion-related reaction, demyelination, congestive heart failure, infection).

✓ 24. Subject must have discontinued all biologic or non-biologic targeted immunomodulatory (TIM) therapies prior to the first dose of study drug. Subject must not have been treated with any of the approved biologic agents infliximab, adalimumab, golimumab, vedolizumab within 8 weeks prior to Baseline, OR with ustekinumab within 12 weeks prior to Baseline. Subjects must not have been treated with tofacitinib, filgotinib, upadacitinib, or ozanimod within 14 days prior to Baseline.

Note: If there is proper documentation of an undetectable drug level measured by a commercially available assay for any of the approved biologics above, there is no minimum washout prior to Baseline.

✓ 25. Subject must not be on immunomodulators (AZA, mercaptopurine [6-MP], methotrexate [MTX]) unless they have been on the course for at least 42 days prior to Baseline and have been on a stable dose for at least 30 days prior to Baseline.

✓ 26. Subject must not receive cyclosporine, tacrolimus, or mycophenolate mofetil (unless for ocular application) within 30 days prior to Baseline.

✓ 27. Subject must not receive oral aminosalicylates or oral UC-related antibiotics within 14 days prior to Baseline unless they have been on stable doses for greater than 14 days prior to Baseline.

✓ 28. Subject must not have received oral corticosteroids unless they have been on that corticosteroid for at least 14 days prior to Baseline and on a stable dose for at least 7 days prior to Baseline. Subjects taking oral corticosteroids must not be taking oral corticosteroids at the following doses: budesonide $>$ 9 mg/day, beclomethasone $>$ 5 mg/day, prednisone or equivalent $>$ 20 mg/day.

✓ 29. Subject must not receive the following therapies within 14 days prior to Screening or during Screening:

- A combination of 2 or more of the following: oral budesonide, oral beclomethasone, and/or oral prednisone (or equivalent) simultaneously, with the exception of inhalers;

- IV corticosteroids.

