5.4 Prior and Concomitant Therapy

Any medication or vaccine (including over-the-counter or prescription medicines, vitamins, and/or herbal supplements) that the subject is receiving at the time of enrollment or receives during the study must be recorded from the Screening Visit through the 30-Day Follow-Up Visit. Additionally, medications taken for UC since the date of diagnosis (based on subject recollection and available medical records) should be entered into the appropriate eCRF inclusive of the dates of first and last dose, maximum dosage taken, and route of administration.

Any questions regarding concomitant or prior therapy should be raised to the AbbVie emergency contact. Information regarding potential drug interactions with ABBV-668 are provided in the current ABBV-668 Investigator's Brochure.

Subjects must be able to safely discontinue any prohibited medications as specified in the eligibility criteria; where not specified, discontinuation must occur 5 half-lives or 4 weeks prior to initial study drug administration. Subjects must be consented for the study prior to discontinuing any prohibited medications for the purpose of meeting study eligibility.

Subjects taking oral aminosalicylates, immunomodulators, oral corticosteroids, and/or UC-related antibiotics at Baseline must continue their concomitant treatment for the duration of the treatment period (through Week 16). Initiating and/or increasing doses of oral aminosalicylates, immunomodulators, oral corticosteroids, and/or UC-related antibiotics during the study is prohibited through Week 16. Decreasing doses of oral aminosalicylates, immunomodulators, oral corticosteroids, and/or UC-related antibiotics during the treatment period is prohibited, except in the event of moderate-to-severe treatment related toxicities and after discussion with the AbbVie TA MD.

COVID-19 Pandemic-Related Vaccination Guidance

Given the ongoing COVID-19 pandemic, selected non-live vaccines (e.g., messenger ribonucleic acid, non-replicating viral vector, protein subunit) to prevent SARS-CoV-2 infection may be administered during screening, the treatment period, or follow up, as long as components of the vaccine are not contraindicated.

The decision to receive a locally available vaccine should be based on local guidance and an individual discussion between the treating physician and the subject.

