Neurologic Symptoms: Subjects with new onset related seizure(s) should be discontinued from study drug and should undergo appropriate prompt diagnostic evaluation and intervention. For subjects who develop clinically significant new onset tremor or other neurological condition considered related to study drug by the investigator, study drug interruption or discontinuation should be considered if the symptoms are severe (CTCAE Grade 3 or higher), persistent or worsening.

Surgery: Subjects who undergo emergency surgery should have study drug interrupted at the time of the surgery. After emergency surgery, reintroduction of study drug is allowed once the physician has examined the surgical site and determined that it has healed and there is no sign of infection.

Laboratory parameter toxicity guidelines are presented in [Table 2](#).

Table 2. Laboratory Parameter Toxicity Guidelines

Laboratory Parameters Toxicity Guidelines		
Absolute neutrophil count (ANC)	< 1000 cells/ μ L	Interrupt study drug dosing and redraw lab with a new sample. 
• If value is confirmed, continue to withhold study drug until value returns to normal reference range or baseline value.
	< 500 cells/ μ L	Interrupt study drug dosing and redraw lab with a new sample. 
• If value is confirmed, discontinue study drug.
Absolute lymphocyte counts (ALC)	< 500 cells/ μ L	Interrupt study drug dosing and redraw lab with a new sample. 
• If value is confirmed, continue to withhold study drug until value returns to normal reference range or baseline value.
Platelet count	< 50,000 cells/ μ L	Interrupt study drug dosing and redraw lab with a new sample. 
• If value is confirmed, continue to withhold study drug until value returns to normal reference range or baseline value.
ALT or AST	ALT or AST > 8 \times ULN	Interrupt study drug dosing immediately and redraw lab with a new sample. 
• If value is confirmed, discontinue study drug and complete supplemental hepatic eCRF.
	ALT or AST > 5 \times ULN	Interrupt study drug dosing immediately and redraw lab with a new sample. 
• If value is confirmed for > 2 weeks of duration, discontinue study drug and complete supplemental hepatic eCRF.

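### Section 5.1 sets no entry limit for ANC, ALC, platelets or QTcF, so keeping out a subject already beyond the plan's on-treatment triggers rests on investigator discretion alone (minor, cheap to fix)

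*Protocol*

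**What the plan says.** **Entry.** Criterion 3 (Protocol Section 5.1) requires laboratory values "meeting the following criteria within the screening period prior to the first dose of study drug" and names two: hemoglobin of at least 8 g/dL, and AST and ALT of at most 2 × ULN. Criterion 5 adds a floor of 90 mL/min for the "Estimated glomerular filtration rate (eGFR) calculated by Cockcroft-Gault". Criterion 19 is the general clause. It excludes a subject who has a condition, or gives the investigator any other reason, that "would make the subject an unsuitable candidate to receive study drug". It contains no number.

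**On treatment, counts (Section 6.2, Table 2).** An ANC below 1000, an ALC below 500 or a platelet count below 50,000 cells/µL leads to interruption and a redraw, then: "If value is confirmed, continue to withhold study drug until value returns to normal reference range or baseline value". For an ANC below 500 cells/µL the rule is "If value is confirmed, discontinue study drug", with no reference to baseline.

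**On treatment, ECG (Operations Manual 3.7).** A confirmed absolute QTcF above 500 msec requires stopping study drug. This is listed separately from the rule on a change of more than 60 msec from Baseline.

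**Baseline value (Operations Manual 3.13).** For each laboratory test it is the last measurement before the first dose. Under footnote c of Operations Manual 2.1 the Screening sample can serve if it is no more than 14 days old and the subject's health has not changed.

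**Background therapy.** Criterion 23 includes "liver enzyme abnormalities, lymphopenia, infection" among its examples of intolerance to immunosuppressants. Criterion 25 bars AZA, 6-MP and MTX "unless they have been on the course for at least 42 days prior to Baseline", with a stable dose for at least 30 days. Section 5.4 then keeps subjects on that treatment through Week 16, apart from a narrow exception for moderate-to-severe treatment-related toxicity.

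**The concern.** The protocol treats four measurements as serious enough to interrupt or stop dosing at a fixed value. All four are available at Screening: hematology and a 12-lead ECG are scheduled there, and QTcF is calculated for every ECG. Yet no entry criterion uses them. A subject who already lies past a trigger meets every numeric entry limit and can be exposed to an investigational drug. The on-treatment rule then does one of two unhelpful things. It may release the subject to continue below the trigger, or it may stop the subject permanently although nothing has changed. What is at stake is subject safety and the consistency of the safety rules, not the efficacy result.

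**Working it through.** No sample-size or power arithmetic applies. The check sets the entry criteria beside the on-treatment rules and follows subjects whose value on treatment equals their value at entry.

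**Step 1: entry limits.** Criteria 1 to 39 contain three numeric organ-function or hematology limits (hemoglobin, AST/ALT, eGFR). None names ANC, ALC, platelets or QTcF.

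**Step 2: apply each rule to an unchanged value.** The entry values below are illustrative.

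| On-treatment rule | Entry limit | Entry value, unchanged | Result |
|---|---|---|---|
| ANC 500-999 cells/µL: hold | none | 700 | Interrupted and redrawn; value is already at baseline, so dosing can resume below 1000 |
| ALC < 500 cells/µL: hold | none | 450 | Same; dosing can resume below 500 |
| Platelets < 50,000 cells/µL: hold | none | 45,000 | Same; dosing can resume below 50,000 |
| ANC < 500 cells/µL: stop | none | 450 | Permanent stop once confirmed |
| QTcF > 500 msec: stop | none | 505 msec (change 0) | Permanent stop once confirmed |

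All five rules lack an entry counterpart. Three are holds that an unchanged value releases, and two are permanent stops.

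**Step 3: a true fall.** A subject enters with ALC 450 and falls to 350. The drug is withheld, and the release condition is met again at 450, still below 500.

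**Step 4: exposure before the first scheduled check.** Dosing is twice daily. The first scheduled on-treatment hematology is at Week 2: 14 × 2 = 28 doses (11 × 2 = 22 to 17 × 2 = 34 with the ±3 day window). The first scheduled on-treatment ECG is at Week 4: 28 × 2 = 56 doses (25 × 2 = 50 to 31 × 2 = 62). These counts assume that nobody orders an earlier recheck, which the Operations Manual permits.

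**Step 5: effect on SAP tables.** SAP Table C-1 uses the same count cut-offs as Table 2 in other units: 1000 cells/µL = 1.0 × 10⁹/L, 500 cells/µL = 0.5 × 10⁹/L and 50,000 cells/µL = 50.0 × 10⁹/L. Its note counts a post-baseline value only if it is more extreme than Baseline, so an unchanged low count is not flagged. No SAP table depends on this point.

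**The case against.** The strongest reply is that the route to exclusion exists. Criterion 19 binds like any other criterion, and an investigator who sees a Screening value at which the protocol requires stopping has a clear reason to use it. A trained physician reads every ECG, extra hematology may be drawn at any visit, and the sponsor reviews laboratory and ECG data for all enrolled subjects. Much of this stands. It is why entry at ANC below 500 cells/µL or QTcF above 500 msec should be regarded as rare, and why the point is minor. It does not close the gap, because the clause gives no value and two sites may apply it differently. For renal function the sponsor did not rely on it: the numeric eGFR limit was added in protocol Version 2.0.

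A second reply is that the return-to-baseline clause has an ordinary purpose. It allows a subject whose baseline is below normal but above the trigger to resume, and its wording presupposes a fall. That purpose is sound. However, Step 3 is a genuine fall and still ends in resumption below the trigger. If an unchanged value could not count as a return, the subject would instead be held until normal with no change in condition, which is no better.

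Third, the lymphopenia in criterion 23 is a past intolerance of unstated degree, and nothing in the documents points to very low neutrophils or platelets, or to a long QTcF, at entry. That is correct. Only low ALC has a plausible route in the text, through continued AZA, 6-MP or MTX.

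A reader might also infer that the plan normally matches entry limits to its own triggers and lapsed here, since hemoglobin entry equals the SAP reporting cut-off and ALT/AST entry lies below Table 2's lowest liver trigger. The documents do not support that. The two examples use different comparators, hemoglobin has no Table 2 row, ALT/AST entry differs from its SAP cut-off of 5 × ULN, and most SAP chemistry variables have no entry limit. The plan states no such rule.

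**Conclusion.** The gap is real and minor. Followed as written, the rules allow a subject with ALC below 500, ANC 500-999 or platelets below 50,000 cells/µL to be dosed, and dosed again, below the level at which the plan says to interrupt. They also allow entry at a value that requires a permanent stop; that case is probably rare and would usually be caught under criterion 19. The conclusion rests on the text of the rules alone. The documents give no frequency of such values at Screening, and none is assumed. A reader might infer harm to the primary endpoint, the sample size or the safety tables. Nothing in the documents supports that.

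**What to change.** Add to criterion 3, at Screening: ANC ≥ 1000 cells/µL, ALC ≥ 500 cells/µL and platelets ≥ 50,000 cells/µL. Add a separate exclusion for QTcF above 500 msec on the Screening ECG, confirmed on repeat, because the stop rule also needs a confirmed value. These are minimum limits taken from the plan's own triggers. A subject just inside them is still one fluctuation away from a hold or stop, so stricter values are a matter for the sponsor's medical judgment. A count that falls between Screening and Baseline remains uncovered. No SAP change is needed.

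The cost is four lines in Section 5.1, no new Screening procedure beyond a repeat ECG where one is needed for confirmation, and a few more screen failures. The change is a protocol amendment and needs IEC/IRB approval before use (Section 8.1); the synopsis lists 23 sites. The SAP version history of September 2024 already refers to enrolled subjects in the past tense. If enrollment has closed, the change is useful only for a later study.

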5.2 Contraception

Contraception Requirements for Females

Subjects must follow contraceptive guidelines as specified:

- Females, Non-Childbearing Potential

Females do not need to use birth control during or following study drug treatment if considered of non-childbearing potential due to meeting any of the following criteria:

1. Premenopausal female with permanent sterility or permanent infertility due to one of the following:

- Permanent sterility due to a hysterectomy, bilateral salpingectomy, bilateral oophorectomy
- Non-surgical permanent infertility due to Mullerian agenesis, androgen insensitivity, or gonadal dysgenesis; investigator discretion should be applied to determining study entry for these individuals.

2. Postmenopausal female

- Age > 55 years with no menses for 12 or more months without an alternative medical cause.
- Age ≤ 55 years with no menses for 12 or more months without an alternative medical cause AND a follicle-stimulating hormone (FSH) level \geq 30 IU/L.

- Females, of Childbearing Potential
 - Females of childbearing potential must avoid pregnancy while taking study drug and for at least 30 days after the last dose of study drug.
 - Females must commit to one of the following methods of birth control:
 - Combined (estrogen and progestogen containing) hormonal birth control (oral, intravaginal, transdermal, injectable) associated with inhibition of ovulation-initiated at least 30 days prior to study Baseline Day 1.
 - Progestogen-only hormonal birth control (oral, injectable, implantable) associated with inhibition of ovulation initiated at least 30 days prior to study Baseline Day 1.
 - Bilateral tubal occlusion/ligation (can be via hysteroscopy, provided a hysterosalpingogram confirms success of the procedure).
 - Intrauterine device (IUD).
 - Intrauterine hormone-releasing system (IUS).
 - Vasectomized partner (provided the partner has received medical confirmation of the surgical success of the vasectomy and is the sole sexual partner of the trial subject).
 - Practice true abstinence, defined as: refraining from heterosexual intercourse when this is in line with the preferred and usual lifestyle of the subject (periodic abstinence [e.g., calendar, ovulation, symptothermal, post-ovulation methods] and withdrawal are not acceptable).

If required per local practices, male or female condom with or without spermicide OR cap, diaphragm or sponge with spermicide should be used in addition to one of the birth control methods listed above (excluding true abstinence).

Contraception recommendations related to use of concomitant therapies prescribed should be based on the local label.

